10.3.5 Post-operative events

Post-operative complications at implant site are assessed at all post-operative visits, with emphasis on:

- Bleeding and/or hematoma
- Hair in-growth
- Skin dehiscence around the abutment

Note: If the event is judged as untoward (exceeding what is normally expected according to surgeon's judgement) it should be reported as an adverse event.

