The primary endpoint of this investigation is the ‘capability of implant/abutment complex to provide a reliable anchorage for the sound processor at three months after MONO surgical procedure’. The primary endpoint will be presented by a point estimate (of the proportion) combined with a two-sided 95% CI, to reflect the level of successful implant/abutment complex installations using the MONO surgical procedure. Assuming a ‘success rate’ of 85% (conservative approach) three months after surgery, and with a confidence interval width of 20% points, the sample size needed is 50 patients. With a proportion of loadable implant/abutment complexes at three months of 95%, the resulting CI would be 11%.

Based on the above, the sample size was decided to be 50 patients.

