19 ADVERSE EVENTS, ADVERSE DEVICE EFFECTS AND DEVICE DEFICIENCIES

19.1 Adverse Event

An adverse event (AE) is defined as any untoward medical occurrence, unintended disease or injury or any untoward clinical signs (including an abnormal laboratory finding) in subjects, users or other persons, in the context of a clinical investigation, whether or not related to the investigational medical device.

Note 1. This definition includes events related to the investigational medical device or the comparator.

Note 2. This definition includes events related to the procedures involved.

Note 3. For users or other persons, this definition is restricted to events related to the use of investigational medical devices.

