19.1.1 Serious Adverse Event

A serious adverse event (SAE) is an AE that led to any of the following:

- a) death,
- b) serious deterioration in the health of the subject, users or other persons as defined by one or more of the following:
 - 1. a life-threatening illness or injury, or
 - 2. a permanent impairment of a body structure or a body function including chronic diseases, or
 - 3. in-patient or prolonged hospitalisation, or
 - 4. medical or surgical intervention to prevent life-threatening illness or injury or permanent impairment to a body structure or a body function
- c) foetal distress, foetal death or a congenital abnormality or birth defect including physical or mental impairment

Note: Planned hospitalisation for a pre-existing condition, or a procedure required by the CIP, without serious deterioration in health, is not considered a serious adverse event.

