19.3 Reporting of Adverse Event(s)

All health problems*, whether judged as related to the surgery and/or the Ponto products or not, that are reported by the subject, found in medical records or found at the clinic visits must be recorded by the PI, or authorised designee, in the eCRF as an AE, preferably within 5 working days. For events judged as related, i.e. ADEs, additional information is required as specified in eCRF.

**except those defined and excluded from the investigation.*

19.3.1 *Reporting of Serious Adverse Event / (Unanticipated) Serious Adverse Device Effect*

In addition to the information already collected and recorded for AEs/ADEs, there are more detailed information required for SAEs/SADEs/USADEs as specified in eCRF.

For SAEs/SADEs/USADEs the Investigator must:

- Record SAE/SADE/USADEs details in the eCRF immediately, but no later than **24 hours** after becoming aware of the event. An email to Oticon Medical will automatically be generated by the EDC system after investigator signing of the SAE form by the Investigator. In addition, an email shall be sent to responsible clinical trial manager (to notify the SAE/SADE/USADE).
- Follow up the initial SAE/SADE/USADEs information as soon as new information is available.
- Report SAE/SADE/USADEs to the EC according to local requirements (e.g. per event and/or annually). In multicentre investigations this may include the SAE/SADE/USADEs reported from another site; this information will be provided by Oticon Medical, if required.
- Provide Oticon Medical with all SAE/SADE/USADEs related documentation and correspondence to the EC.

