19.4 Non-reportable events

When performing a BAHS surgery, some intra- and post-operative events are more or less likely to occur (i.e. not 'untoward' per se) (see sections 10.2.3 and 10.3.5). Therefore, in this investigation, the following events will be captured in the eCRF on the applicable study visit. To avoid double-reporting, these events will not be recorded in the AE log, unless the investigator judges them to exceed the level of what is to be expected (i.e. 'untoward' per se):

During surgery;

- Drilling into veins
- Drilling into air pockets
- Dura mater exposed

Post-operative complications

- Bleeding or hematoma
- Pain or numbness
- Skin dehiscence
- Erythema
- Edema
- Granulation tissue
- Skin reactions
- Revision surgery

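### Section 19.4 keeps revision surgery out of the AE log with no override for seriousness, and no count of revisions is assured

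*Combined protocol and SAP*

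**What the plan says.** Section 19.4 sets apart a group of intra- and post-operative events that it regards as not untoward in themselves. The last post-operative entry is "Revision surgery". On recording, it says that "the following events will be captured in the eCRF on the applicable study visit". To avoid reporting the same event twice, it adds that "these events will not be recorded in the AE log, unless the investigator judges them to exceed the level of what is to be expected".

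Three other provisions decide what follows from that exemption:

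- Section 19.1 defines an AE as "any untoward medical occurrence, unintended disease or injury or any untoward clinical signs", so an event must be untoward to qualify.
- Section 19.1.1 defines an SAE as an AE with one of several consequences. These include in-patient or prolonged hospitalisation and "medical or surgical intervention to prevent life-threatening illness or injury or permanent impairment to a body structure or a body function".
- Section 19.3 requires all health problems to be recorded as AEs, "except those defined and excluded from the investigation". The 24-hour notice in 19.3.1 applies to SAEs, SADEs and USADEs only.

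The safety endpoint (sections 8.3, 10.4 and 12.3) is built from adverse events and device deficiencies. The primary composite (sections 8.1 and 10.3.1) has five components assessed at three months, and re-operation is not one of them. Section 12.4 counts loss of the implant, by extrusion or elective removal, as a failure.

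**The concern.** The exemption turns on whether a revision was expected, whereas 19.1.1 turns on what an event led to. These are different questions, and 19.4 does not say which prevails. The protocol states no expected revision rate, and section 7.1.2 says that the probability of harm could differ with this kit and that the final design has no clinical data yet. Investigators at seven sites would therefore judge expectedness without a stated reference.

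Two things are at stake. A second operation that is serious under 19.1.1 may not start the 24-hour notice or enter the AE tables. In addition, the primary result is meant "to reflect the level of successful implant/abutment complex installations using the MONO surgical procedure", and a reader of that figure would want to know how many installations needed another operation to reach it.

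**Working it through.** **1. Following an expected revision through the definitions.** Suppose the investigator judges a revision to be within expectation.

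- Under 19.4 it is not untoward and stays out of the AE log.
- It therefore does not meet 19.1, and the exception in 19.3 takes it out of the general recording rule.
- Since 19.1.1 starts from an AE, the revision itself cannot be classed as an SAE, even with hospitalisation.
- The 24-hour step in 19.3.1 is then not triggered by the revision.

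One route stays open. The condition that led to surgery may be an AE in its own right, with surgery as its consequence. Skin overgrowth is not on the 19.4 list, so it remains reportable. Granulation tissue, pain and skin reactions are on the list. The route is closed when the underlying condition is also listed and is also judged expected.

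**2. Does the double-reporting rationale fit?** The other seven post-operative entries each have a named assessment:

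| 19.4 entry | Assessed in |
|---|---|
| Bleeding or haematoma | 10.3.5 |
| Skin dehiscence | 10.3.5; section 8.2, row E |
| Pain or numbness | 10.3.6, 10.3.7; rows G and H |
| Erythema, oedema, granulation tissue | IPS and Holgers, 10.3.4 |
| Skin reactions | Holgers, 10.3.4.2 |
| Revision surgery | no item names it as an outcome |

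Section 10.3.5 says "Post-operative complications at implant site are assessed at all post-operative visits, with emphasis on" and then names bleeding or haematoma, hair in-growth and dehiscence. That wording is not exhaustive, so a revision could be entered there and appear under row F of section 8.2, but nothing requires it. Revision is also mentioned in the IPS treatment advice (10.3.4.3). The planned comparison of treatment given with that advice evaluates the scale and does not yield a count of revised implants.

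**3. The composite.** Removal of the implant fails (12.4). A revision before month 3 that leaves the implant in place, stable and usable gives Yes on every component. Abutment exchange is unclear: the synopsis and 8.1 require the whole implant/abutment complex to be in place, while 10.3.1 asks only about the implant.

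**4. Size.** The sample size fixes the denominator. Section 12.2 assumes 85% success and a 95% CI 20 points wide:

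n = p(1−p)(2 × 1.96 / width)² = 0.85 × 0.15 × (3.92 / 0.20)² = 48.98, so 49 against the stated 50. At n = 50 the width is 3.92 × √(0.1275 / 50) = 19.8 points. The stated size is reproduced closely.

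With 50 implants, one case moves a revision-free success rate by 1/50 = 2.0 points. Bilateral implants count separately, so the step shrinks slightly if there are more; with an assumed 55 it is 1/55 = 1.8 points.

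The documents give no revision rate, so the following only illustrates scale. From an assumed 48/50 on the primary definition, with exact (Clopper-Pearson) 95% CIs:

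| Successes that had a revision (assumed) | Success without revision | 95% CI |
|---|---|---|
| 0 | 48/50 = 96.0% | 86.3 to 99.5 |
| 1 | 47/50 = 94.0% | 83.5 to 98.7 |
| 2 | 46/50 = 92.0% | 80.8 to 97.8 |
| 3 | 45/50 = 90.0% | 78.2 to 96.7 |

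The chance of at least one revision among 50 independent implants is 1 − (1 − r)^50. For assumed r of 1%, 2%, 4% and 6% it is 39%, 64%, 87% and 95%.

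**The case against.** The strongest reply is that revisions are neither hidden nor beyond reporting. They go on the eCRF visit form. Section 13.2 asks for data entry within 5 working days, and section 11.1 provides for remote review, so the sponsor should learn of them. An investigator may log any revision thought to exceed expectation. Surgery is usually the consequence of an event, and the event itself may be logged. All of this stands. It limits the gap to the formal AE/SAE route, the 24-hour timing and the absence of an assured count.

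A reader might infer that no expected revision can ever lead to an SAE, or that revisions would show as zero related AEs. The text does not support either: both require that the underlying condition also goes unlogged, and the second requires every investigator to judge every revision expected.

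A reader might also infer that the primary proportion is biased upward. That is not shown. Section 9.1 presents the endpoint as usability of the device at three months, and a complex that is usable after revision meets that definition. Success without revision is a different quantity, useful beside the primary one.

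Finally, section 12.3 leaves detail to a statistical analysis plan, which could specify a revision table. Nothing in the text available does so, and such a table would not close the reporting gap in 19.4.

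**Conclusion.** The point holds in a limited form. Sections 19.1.1 and 19.4 are not reconciled: applied as written, a revision judged expected that meets a seriousness criterion can miss the 24-hour notice and the AE-based safety endpoint, unless its underlying condition is logged separately. Not every revision would meet such a criterion. The rationale of avoiding double reporting does not fit this entry, because no other item is sure to count it.

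For the primary endpoint the issue is visibility. It concerns revisions before month 3 that leave the implant in place, and the status of abutment exchange is unclear. Each such case separates the primary figure from a revision-free figure by 2 points if there are 50 implants. How many will occur cannot be judged from the documents. The reporting gap rests on the wording alone and does not depend on any assumed rate.

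**What to change.** - Remove revision surgery from the 19.4 list. At minimum, add one sentence: any event covered by 10.2.3, 10.3.5 or 19.4 that meets a 19.1.1 criterion is reported under 19.3.1 whether or not it was expected.
- Tabulate the number and proportion of implants revised by 3 and by 12 months, with the reason.
- Report 3-month success without revision surgery as a supplementary figure, with its 95% CI, and leave the primary endpoint as defined.
- Align the wording of component I in the synopsis, 8.1 and 10.3.1, so that the scoring of an abutment exchange is settled before analysis.

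The cost is a small text change, two or three table rows and a few more AE or SAE forms. The supplementary rate may look less favourable than the primary one. No visit or procedure is added.

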19.5 Safety event follow-up

Medical follow-up of any type of safety event will continue until the abnormality resolves, or an adequate medical explanation is apparent.

Documentation of all follow-up information regarding the AEs must be provided in the eCRF and, in accordance to the reporting requirements described above.

If the subject is withdrawn from study treatment due to an AE, the AE and the reason for withdrawal from the study is to be documented clearly in the eCRF.

CONFIDENTIAL

oticon MEDICAL	Title BC108 CIP MONO	Document no Doc-00068506	Revision 2	Page 44(48)
--------------------------	--------------------------------	------------------------------------	----------------------	-----------------------

20 SUSPENSION OR EARLY TERMINATION OF THE CLINICAL INVESTIGATION

The investigator or sponsor may at any time terminate the clinical investigation due to circumstances related to the rights, safety and welfare of the subjects enrolled, or to the conduct of the investigation by an investigator/investigational site or sponsor, that preclude ongoing subject treatment.

If the investigation is suspended or terminated prematurely, the investigator will promptly inform the sponsor and provide the reason(s) thereof (and vice versa). The ECs concerned will also be informed promptly in writing by the investigator.

21 PUBLICATION POLICY

A description of this clinical investigation will be available, throughout the whole duration and onwards, on www.ClinicalTrials.gov.

When the clinical investigation is completed, even if prematurely terminated, a final report will be compiled. The results obtained in the investigation will be submitted for publication in scientific journals by the investigators, in cooperation with the Sponsor. Three-months and 1-year results could be published together or separately. The coordinating investigator will be responsible for drafting of a manuscript on the combined results in a joint, multicentre publication. Results derived from individual sites cannot be published until after the joint results are published. Privacy and confidentiality of information about each subject will be preserved in any reports and any publications of the clinical investigation data. During the course of the study, annual progress reports will be submitted to the ECs as applicable.

